13.7.3 Follow-up Procedures

After the last patient has completed visit 7, there will be an interim deadlock, at which point we will analyse the primary endpoint data.

At 1 year post-transplant the patient's medical records will be reviewed for the following data which will be extracted: Graft function as measured by eGFR and serum creatinine Episodes of rejection Episodes of infection Diabetic control measured by HbA1c

Current anti-diabetic medication regimen

We will then perform a secondary data analysis.

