11.3.2 Secondary Endpoints

- 1) Histological staining for Treg cells in renal biopsy tissue between baseline and 3 month protocol biopsy
- 2) Incidence of delayed graft function, defined as the need for dialysis within 1 week post-transplant
- 3) Diabetic control between baseline and month 3 using change in HbA1c measurement
- 4) Dose of other anti-diabetic medication between baseline and month 3 (descriptive)
- 5) Safety endpoints: i.e. number of hypoglycaemic episodes (descriptive)
- 6) Insulin resistance: HOMA IR measurement at month 3
- 7) Graft function: (eGFR) at month 3
- 8) Episodes of acute rejection (defined as biopsy proven acute rejection)
- 9) Episodes of opportunistic infections: bacterial and viral (descriptive)

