11.4 Exploratory or Tertiary Endpoints/outcomes

- 1) 12-month graft function (eGFR) and diabetic control (HbA1c; medication review) to assess legacy effect (potential follow up publication)
- 2) Differences in other peripheral T cell populations, measured by FACS analysis
- 3) Histological staining for Treg cells in any renal biopsy taken for clinical indications between baseline and month 3 protocol biopsy
- 4) Differences in the functional phenotype of the Treg cells

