11.5 Objectives and Endpoints Summary

Objective	How objective measured	Outcome
Examine the effect of AZD1656 on Treg cell migration	Change in peripheral Treg population between randomisation and month 3 measured by mean change in Treg cell number between baseline and 3 months using FACS analysis.	Does AZD1656 lead to enhanced migration as demonstrated by a fall in peripheral Treg population over time compared to placebo?
Examine the effectiveness of AZD1656 on diabetic control	Change in HbA1c between baseline and month 3 visit, HOMA-IR at month 3, descriptive change in anti diabetic medication dose/need for additional anti-diabetic therapy.	Is there a difference between placebo and IMP on diabetic control/insulin resistance?
To investigate the effect of AZD1656 on renal transplant function	Renal function (eGFR CKD EPI) measured at 3 months and 12 months.	Is there a difference between AZD1656 and placebo treated patients' renal function at 3 and 12 months?
To determine the safety of AZD1656 to control diabetes post- transplant.	Patient and graft survival, number and type of AE (hypoglycaemic episodes, infective episodes), number and type of SAE, rejection rates (defined as incidence of biopsy proven acute rejection)	Is there a difference between placebo and AZD1656 treated groups in terms of number of AE, SAE, renal function and rejection rates?
Effect of AZD156 on Treg cell infiltration in renal transplant tissue	Change in Treg staining on renal biopsies collected as standard of care at implantation and 3 months post transplant.	Is there a difference between placebo and AZD1656 treated groups in terms of change in Treg cell infiltration between baseline and 3 month transplant biopsy?

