13.7 Trial Schedule

13.7.1 Schedule of Assessment (in Diagrammatic Format)

Schedule of									Data
visits	Screening	Visit 1	Visit 2	Visit 3	Visit 4	Visit 5	Visit 6	Visit 7	review
Day/Month	Before or	Randomisati	week 1	week 2	week 4	week 8	week 12	2 weeks after	1 yr post
	within 24h	on up to 24h	post	post	post	post	post	stopping	transplan
	post	post	randomisat	randomisat	randomisat	randomisat	randomisat	study	+/- 2
	transplant	transplant	ion (+/- 3	ion (+/- 3	ion (+/- 3	ion (+/- 1	ion (+/- 1	medication	, – weeks
	transplant	transpiant	days)	days)	days)	week)	week)	(+/- 1 week)	WEEKS
Informed								(1) = 110011	
Consent	Х								
Inclusion/									
exclusion									
criteria	Х	x							
Negative									
pregnancy test	х	x	х	х	x	x	x	x	
pregnancy test	^	^	^	^	^	^	^	^	
Demographics	х								
Transplant									
data		х							
Medical									
	Y								Х*
history	x								X*
Randomisation		x							
Study drug									
dispense		x							
Drug									
accountability			х	х	х	х	х		
Dhusiaal									
Physical									
examination		X	X	X	x	x	X	X	
Weight		х	х	х	х	х	х	х	Х*
Vital signs		x	х	х	x	x	x	х	Х*
Concomitant									
medication	X	X	X	X	X	X	X	X	X*
Laboratory									
bloods**		x	x	x	x	x	x	x	Х*
Placed for Two									
Blood for Treg									
quantification		x	x				x	x	
AE assessment		X	X	X	x	x	x	X	Х*
End-point									
assessment							x		

*At this review, the patient's medical records will be reviewed and their clinical data extracted to include:
Graft function as measured by eGFR and serum creatinine
Episodes of rejection
Episodes of infection
Diabetic control measured by HbA1c
Vital signs
Weight
Current medication and anti-diabetic medication regimen

**Laboratory bloods: including fasting c-peptide, cholesterol and serum glucose; serum urea and electrolytes (including creatinine), albumin, alkaline phosphatase (ALP), bilirubin, alanine aminotransferase (ALT), bone profile and C-reactive protein; haemoglobin and HbA1c; and serum save +/- blood for peripheral Tregs as per protocol. The serum save will be taken and processed in keeping with normal protocols but will be used for functional assays to measure the activity of the Tregs at different time points.

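### Patient and graft survival, named in section 11.5, are missing from the endpoint lists and the 1-year extraction lists, and eGFR has no rule after death or graft failure, so the arm losing more grafts can look equal or better.

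*Combined protocol and SAP*

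**What the plan says.** **Objectives table.** In section 11.5 (Objectives and Endpoints Summary), the safety row is measured by "Patient and graft survival, number and type of AE (hypoglycaemic episodes, infective episodes), number and type of SAE, rejection rates". No time point, definition or analysis is given for survival. The outcome question in the same row is "Is there a difference between placebo and AZD1656 treated groups in terms of number of AE, SAE, renal function and rejection rates", which leaves survival out.

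**Endpoint lists.** Graft function appears in section 11.3.2 as "Graft function: (eGFR) at month 3" and in section 11.4 as "12-month graft function (eGFR) and diabetic control (HbA1c; medication review) to assess legacy effect". Patient survival and graft survival are in neither list. Section 19.3 repeats both lists. It assigns acute rejection, opportunistic infections and the 12-month exploratory endpoint to the second data analysis.

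**1-year data.** Section 13.7.3 lists "Graft function as measured by eGFR and serum creatinine Episodes of rejection Episodes of infection Diabetic control measured by HbA1c", followed by the current anti-diabetic regimen. The footnote to the schedule in section 13.7.1 begins "At this review, the patient's medical records will be reviewed and their clinical data extracted to include" and adds vital signs, weight and current medication. Neither list names death, return to dialysis, graft nephrectomy or re-transplant.

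**Analysis.** Section 19.5 specifies intention to treat, a normality test, and then an unpaired t-test or Mann-Whitney test for continuous variables. Section 19.6 names no further test. Section 19.9 expects no loss to follow-up and relies on the team's efforts to correct missing data. None of these sections mentions death or graft failure.

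**The concern.** A measure promised in one section has no counterpart in the sections that govern data collection and analysis. That would be only an alignment matter if eGFR could carry the information by itself, but it cannot. A patient who has died has no eGFR. A patient back on dialysis has either no value or one based on a creatinine that dialysis has altered. The worst graft outcomes can therefore leave the graft-function comparison, and if the grafts that fail are the weaker ones, their removal raises the mean of the arm that lost them.

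Section 9.3 presents Treg localisation as a marker for improved graft survival, and section 19.1 says the pilot is meant to generate data for a larger trial. A graft-function result that is blind to graft loss is a poor basis for that decision. Leaving the handling of these patients open until the data are in also makes the choice look data-driven.

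**Working it through.** **Step 1. Plan's own figure.** Section 19.1 gives 25 per arm, chosen for feasibility; 2 x 25 = 50 matches the planned total in section 5.0. No power, eGFR standard deviation or graft-loss rate is stated, so there is nothing further to reproduce.

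**Step 2. Tracing the two items.**

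| Place | Patient survival / death | Graft survival / failure |
|---|---|---|
| 11.5, measure | named | named |
| 11.5, outcome question | absent | absent |
| 11.3.2, 11.4, 19.3 | absent | absent, except dialysis within week 1 (delayed graft function) |
| 13.7.1 footnote, 13.7.3 | not named | not named |
| AE/SAE records (17.1, 17.4, 17.7) | captured as an SAE | recordable as an AE or SAE, but undefined |
| eGFR rule (19.5, 19.6, 19.9) | none | none |

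**Step 3. Effect on the eGFR comparison.** Assumptions, none of them from the documents: underlying eGFR has mean 50 and SD 15 in both arms, with no true difference; the active arm loses 3 of 25 grafts and placebo loses none.

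If loss is unrelated to underlying eGFR, the expected difference among patients with a value is 50 - 50 = 0. Scoring each loss as 0 gives 50 x 22/25 = 44 in the active arm, a difference of 44 - 50 = -6. With 1 or 2 losses the active mean is 48 or 46, a difference of -2 or -4.

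If weaker grafts are more likely to fail, the remaining mean rises. A simulation of 4,000 trials per scenario gave these mean differences (active minus placebo, mL/min/1.73 m2):

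| Relation of loss to underlying eGFR | Patients with a value | Loss scored 0 | Loss scored 10 | Trials in which the first comparison favours the losing arm |
|---|---|---|---|---|
| none | 0.0 | -6.0 | -4.8 | 51% |
| correlation 0.5 | +1.6 | -4.6 | -3.4 | 64% |
| lowest eGFRs lost | +3.1 | -3.2 | -2.0 | 77% |

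The columns agree with each other up to rounding and simulation error. For the middle row, 51.6 x 22/25 - 50 = -4.6, and adding 3 x 10/25 = 1.2 gives -3.4. The score of 10 stands in for a low dialysis-period value, and under it the loss does show. With 5 v 1 losses the first column becomes 0.0, +2.0 and +3.8, and zero scoring gives -8.0, -6.5 and -5.1.

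**Step 4. Could graft loss be tested on its own?** The normal approximation at two-sided 0.05 is

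power = Phi{ [ d - 1.96 x sqrt(2 x pbar x (1 - pbar)/n) ] / sqrt([p1(1 - p1) + p2(1 - p2)]/n) },

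where d is the absolute difference in proportions and n = 25. For 4% v 16%: (0.12 - 1.96 x 0.0849)/0.0831 = -0.56, so power is about 29%. For 4% v 24% it is about 53%. Fisher's exact test gives p = 0.61 for 1 v 3 losses and p = 0.11 for 0 v 4. These rates are also assumed. Survival can only be descriptive here.

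**The case against.** The case for leaving the plan alone has real substance, and it rules out several stronger readings that a reader might infer.

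- *Deaths and graft losses go unrecorded, or return to dialysis is caught only if serious.* Not supported. Section 17.1 makes death an SAE and defines an AE as any untoward medical occurrence. Section 17.4 puts non-serious AEs in the CRF and has source records reviewed at least monthly during treatment. The schedule marks AE assessment and medical history at the 1-year review. Dialysis in the first week is itself a secondary endpoint.
- *The 1-year list is closed.* Section 13.7.3 reads that way, but the 13.7.1 footnote is worded as a list of inclusions.
- *The plan prescribes a survivors-only eGFR analysis.* It does not. Section 19.5 says intention to treat, creatinine is collected, and a dialysis-period value could enter. The plan is silent on which applies.
- *Section 11.5 poses a 12-month survival question that will go unanswered.* It gives survival no time point, and its outcome question omits it.

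In addition, eGFR is one of nine secondary endpoints at month 3 and exploratory at month 12, while the primary objective is Treg migration. Section 19.3 also refers to a SAP for full details, and the document reviewed holds no separate SAP text; a rule could exist there.

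What remains is narrower. AE records give no definition of graft failure, no dedicated field and no planned comparison by arm. The monthly record check is tied to the 3-month treatment period. A stated intention to treat does not say what value a patient without an eGFR receives. A separate SAP could supply the eGFR rule, but the protocol's endpoint and extraction lists would still need to match section 11.5.

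**Conclusion.** The point holds as a gap in definition, alignment and analysis, not as an absence of capture. Survival is named as a safety measure in section 11.5 and then not carried through, and the eGFR comparisons have no rule for death or graft failure. Deaths necessarily leave those comparisons; failed grafts may.

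Under the assumed mean of 50, SD of 15 and 3 v 0 losses, the comparison among patients with a value averages 0 to +3 in favour of the arm losing grafts, against -3 to -6 with losses scored 0. The sign and rough size depend on those assumptions and on failed grafts having no value. If a low dialysis-period value is used instead, part of the loss appears. The documents give no loss rate, so how often this would matter is unknown; with no deaths or graft failures it would not arise. This is a worthwhile, inexpensive improvement to secondary and exploratory analyses and does not affect the primary endpoint.

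**What to change.** 1. Add date of death and date and type of graft failure (return to maintenance dialysis, graft nephrectomy, re-transplant) to the 1-year extraction in sections 13.7.1 and 13.7.3. Have the same items complete at the first datalock, because month-3 eGFR is analysed then.
2. Align sections 11.3.2, 11.4 and 19.3 with section 11.5 by reporting deaths and graft failures by arm, descriptively and with a stated time point.
3. For month-3 and month-12 eGFR, assign graft failure and death the worst ranks in the Mann-Whitney test already named in section 19.5, stating in advance how the two are ordered. Report the analysis of functioning grafts only as a sensitivity analysis. Scoring failed grafts as 0 in a mean is a debatable choice and, if wanted, also belongs among the sensitivity analyses.

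The cost is a few fields in a records review already planned and one paragraph of analysis text. The downside is that, when such events occur, the eGFR comparison becomes rank-based and no longer yields a simple difference in mL/min/1.73 m2. No visit or element of care changes.

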13.8 Withdrawal criteria

Study medication will be stopped in the following situations:

- 1. Hypoglycaemia despite removal of other glucose-lowering drugs: e.g. repeated events of minor hypoglycaemia defined as:
 - An episode with symptoms and confirmed low glucose (<3.9 mmol/L).
 - An episode with low glucose (<3.9 mmol/L).

- An episode with symptoms suggestive of hypoglycaemia when glucose was not measured.

If a patient has episodes of hypoglycaemia, their anti-diabetic medications will be altered as per standard of clinical care.

2. One event of major hypoglycaemia regardless of any other diabetes drugs, as defined by the American Diabetes Association (ADA):

- Requires assistance of another person to actively administer carbohydrates, glucagon, or take other corrective actions.

Plasma glucose concentrations may not be available during an event, but neurological recovery following the return of plasma glucose to normal is considered sufficient evidence that the event was induced by a low plasma glucose level

- 3. Impaired hepatic function (AST/ALT >x3 ULN,) due to the hepatic metabolism of AZD1656
- 4. The patient's target HbA1c is less than 6.5% and their other anti-diabetic medications have been withdrawn.

If any of these situations occur, the subject will be withdrawn from the study medication, but will continue in the study with other study related activities.

If the patient's clinical care team feel that the patient requires treatment with gemfibrozil, then the patient will be withdrawn from the study medication, but continue other study related activities. This is not expected to happen in practice as gemfibrozil interacts with other immunosuppression medication the patient takes as part of their standard transplant regime, so gemfibrozil is avoided in transplantation medicine.

Patients may be withdrawn from the study if the investigator feels that individual adverse events or new information gained mean that it is not safe to continue the study, or if it is felt to be in the participant's best interest to stop the study.

Should a participant wish to withdraw from the study treatment, the patient will stop the study medication. Patients would be encouraged to continue with the study visits for safety, however should they not want to take part in any further study visits, they will continue to be followed up by their clinical care team as standard. It should be noted that routine clinical visits are very frequent for patients in their first year posttransplant so it is unlikely that any patients will get lost to follow-up, or be put at risk should they withdraw from the study.

Participants will continue to receive follow up procedures unless they specifically opt out.

Routine clinical data collection will continue for patients who have withdrawn from the study unless they specifically opt out of using routine clinical data collection. Should a patient withdraw from the study this will be documented on the CRF using a study termination form, which includes recording reasons for withdrawal and consent for any follow-up information being collected. This would include a scenario in which a female participant had a positive pregnancy test. We would consent her for monitoring her during her pregnancy.

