12.0 Eligibility Criteria

In order to be eligible for the trial, participants must meet all of the below inclusion criteria and none of the below exclusion criteria.

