12.2 Exclusion Criteria

- a) Unable to consent
- b) Known allergy/intolerance to AZD1656
- c) Pregnant or breastfeeding women
- d) Planning on becoming pregnant/unwilling to use highly effective contraception* during the 3 month treatment period and for 2 weeks afterwards
 - a. In the case of men with sexual partners who are women of childbearing potential: refusal to wear a condom **and** female partner planning on becoming pregnant/unwilling to use highly effective contraception* during the 3 month treatment period and for 2 weeks afterwards
- e) Clinically significant history of abnormal physical and/or mental health as judged by the investigator other than conditions related to chronic kidney disease
- f) Current or planned use of strong inhibitors of CYP2C8
- g) Participation in an investigational drug trial in the 3 months prior to administration of the initial dose of study drug

*Highly effective contraception methods are defined as those that can achieve a failure rate of <1% per year when used correctly and consistently. These include:

- Combined (oestrogen and progestogen containing) hormonal contraception associated with inhibition of ovulation either oral, transvaginal or transdermal
- Progestogen-only hormonal contraception associated with inhibition of ovulation either oral, injectable or implantable
- Intrauterine device (IUD) or intrauterine hormone-releasing system (IUS)
- Bilateral tubal occlusion
- Vasectomised partner provided that the partner is the sole sexual partner of the participant and that the vasectomised partner has received medical assessment of surgical success

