13.0 Trial Procedures

13.1 Participant identification

Participants will be identified by their regular clinical team from those patients admitted or soon to be admitted for a renal transplant. Eligibility decision will be made by the Chief Investigator (CI) or Sub Investigator (Sub-I).

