14.2 Sample Collection/Labelling/Logging

Samples will be collected by the research nurse or trained phlebotomist as per standard of care.

Samples will be labelled with patient identification and sent to the local labs as per routine care and the results logged on the pathology system and transcribed to the CRF.

The only samples that will be sent to the local lab, which are not part of routine care, are for serum C-peptide.

Volume of samples to be collected:

The total volume of blood which will be taken on top of routine care is:

1 table-spoon (approximately 20ml) of blood per clinic visit (4x 6ml samples of blood) in lithium heparin tubes provided locally.

In addition, 20ml of blood will be taken at visit 1, 2, 6 and 7 for Treg quantification via FACS. This sample will be taken to the Royal London Immunology laboratories by members of the study team for processing.

Any biopsy material will be processed and stored as part of routine clinical care.

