17.11 Pregnancy

If a patient becomes pregnant whilst enrolled in the study, the study medication will be withdrawn but the patient will continue on in the study. No data is available on the effects of AZD1656 on pregnancy and lactation in humans. Results from the reprotoxicity studies in animals (fertility and embryo-foetal development) support inclusion of women of childbearing potential in clinical studies, provided that pregnancy is prevented using a reliable form of contraception. The results from the animal studies suggest that any adverse effect observed was as a result of maternal hypoglycaemia.

If a patient on the study medication becomes pregnant the CI has the responsibility to ensure that the pregnancy form is completed and sent to the sponsor within the agreed timelines. The initial report should be sent within 24 hours and follow up information submitted as and when it becomes available up to agreed follow up time after birth.

If a female patient on the study medication, or the female partner of a patient on the study medication, becomes pregnant, she will be asked to sign an additional consent form to allow data collection and monitoring during her pregnancy.

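### Study drug must stop at AST/ALT above 3 x ULN, but no entry criterion sets a liver-enzyme limit, so a patient already above it can be randomised and started

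*Combined protocol and SAP*

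**What the plan says.** Section 13.8 gives four numbered conditions under which study medication is stopped. The third is "Impaired hepatic function (AST/ALT >x3 ULN,) due to the hepatic metabolism of AZD1656". A patient who meets it comes off drug but stays in the study for its other activities. The rule does not distinguish a rise on treatment from a value already high at baseline.

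Entry is governed by section 12.0: "participants must meet all of the below inclusion criteria and none of the below exclusion criteria". The inclusion criteria in 12.1 cover age, transplantation within the previous 24 hours, type 2 diabetes, consent and a pregnancy test. The seven exclusions in 12.2 name no liver test. The nearest is (e): "Clinically significant history of abnormal physical and/or mental health as judged by the investigator other than conditions related to chronic kidney disease".

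Two other reasons for stopping drug do have a counterpart at entry:

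- **Pregnancy.** Section 17.11 says "If a patient becomes pregnant whilst enrolled in the study, the study medication will be withdrawn", and exclusion (c) is "Pregnant or breastfeeding women".
- **Gemfibrozil.** Section 13.8 withdraws study drug if it is needed, and exclusion (f) is "Current or planned use of strong inhibitors of CYP2C8".

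On measurement, ALT is in the laboratory panel at visit 1 (13.7.1 and 13.7.2). Section 14.2 implies that it is routine care: "The only samples that will be sent to the local lab, which are not part of routine care, are for serum C-peptide".

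**The concern.** The reason given for the stopping rule is that the liver metabolises the drug. That reason applies equally to a patient whose enzymes are above the threshold before the first tablet. As written, the entry rules can admit a patient to a drug that the stopping rule says must not be continued. Section 15.15 allows no dose modification, so a lower dose is not available.

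The main issue is a small, avoidable exposure in a patient who should not have been started. There is also some waste. Such a patient is either dosed and then stopped, or is randomised and never dosed. In the second case section 13.4.1 drops the patient without replacement.

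**Working it through.** The protocol gives no figure to reproduce on this point. The check is a comparison of sections, followed by simple arithmetic on the consequences.

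**Step 1. Does any entry criterion set a liver limit?**

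| Section | Content | Liver-enzyme limit |
|---|---|---|
| 12.1 (a)-(e) | 5 inclusion criteria | 0 of 5 |
| 12.2 (a)-(g) | 7 exclusion criteria | 0 of 7 |
| 13.8, item 3 | Stopping rule | 3 x ULN |

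**Step 2. Must a liver result be seen before the first dose?** Section 13.3 lists what is collected after consent and before randomisation: the entry criteria, demographics, transplant data, concomitant medication and medical history. No laboratory result is listed. ALT is first scheduled at visit 1, together with randomisation and dispensing. The visit-1 list in 13.7.2 places bloods ahead of randomisation but does not say that results must be back.

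**Step 3. Which enzyme is measured?** The laboratory panel is scheduled at visits 1 to 7 and includes ALT, which gives 7 scheduled ALT measurements. AST is not in the panel, so it has 0 scheduled measurements although the stopping rule names it.

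**Step 4. What happens to an affected patient?**

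- *Result noticed after dosing.* Exposure per day of delay = 2 doses x 100 mg = 200 mg (dose from 9.3 and 15.13). The patient is then stopped, but remains in the study (13.8) and in the ITT analysis (19.5).
- *Result noticed after randomisation but before dosing.* The patient is not included and not replaced (13.4.1), so 1 of 50 planned places is lost: 1/50 = 2%.

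**Step 5. Effect on the primary comparison (illustrative only).** With 25 patients per arm (19.1), assume that k stopped patients in the active arm show no drug effect at 3 months. Then:

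expected ITT difference = (1 - k/25) x true effect

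- k = 0: 1.00 x true effect
- k = 1: 1 - 1/25 = 0.96, a 4% dilution
- k = 2: 1 - 2/25 = 0.92, an 8% dilution

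Both k and the absence of effect are assumptions. The planned sample size and the 0.05 significance level are unaffected.

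**The case against.** The strongest reply is that the exposure is rare, brief and already controlled. The Chief Investigator or a Sub-Investigator decides eligibility, with medical history in hand, and exclusion (e) lets them keep out known liver disease. ALT is drawn at visit 1, patients are in hospital for the first 5-7 days (9.2), the stopping rule applies as soon as a high result is read, and 15.15 lets the investigator stop drug on safety grounds. The hepatic signal is weak: a minor enzyme increase that could not be ruled out in Phase IIb. The protocol also has no general principle that every stopping condition must be mirrored at entry. Item 4 of 13.8, on target HbA1c, has no matching exclusion either.

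Much of this stands, and it limits the size of the point. Entry of such a patient is possible rather than certain, and the expected harm is small. The safeguards still do not close the gap. Exclusion (e) is discretionary, concerns history, has no threshold and does not call for a current ALT to be reviewed. Inpatient monitoring and the power to stop drug protect the patient only once dosing has begun. An unmatched item 4 does not supply the missing liver criterion.

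A second objection is that a new exclusion would be ineffective unless a separate rule required the result to be seen. This fails. Sections 12.0 and 13.3 already require the exclusion criteria to be settled before randomisation, so a criterion based on ALT would make someone look at the ALT. It is fair to say, however, that waiting for a result uses part of the 24-hour window, and that section 9.2 gives a reason for starting drug early.

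**Conclusion.** The concern holds. The protocol permits a patient with ALT or AST above 3 x ULN to be randomised and started, and then requires study drug to be stopped. This follows from the text and needs no assumption about frequency.

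The size is modest. How often it would happen cannot be estimated, because no baseline enzyme distribution is given. The direct consequence per affected active patient is 200 mg for each day before the result is acted on. The 4% to 8% dilution rests on an assumed one or two patients with no drug effect, and carries no weight in the conclusion. The change is worth making because it is a safety and consistency improvement at very low cost, not because the trial's result depends on it.

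**What to change.** Add one exclusion to section 12.2: ALT (or AST if available) above 3 x ULN on the most recent sample from the transplant admission, including the visit-1 sample. The Chief Investigator or Sub-Investigator checks it within the existing eligibility check before randomisation, and a routine-care result is acceptable. Where there are several results, the most recent one governs. ALT is named first because AST is not on the trial's laboratory list.

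No separate review rule, extra sample, visit or endpoint is needed. ALT is already drawn at visit 1 and goes to the hospital's own laboratory. The costs are a protocol amendment with its usual approvals, an occasional patient screened out, and possibly a short wait for a routine result within the 24-hour window.
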